## **ABSTRACT**

**OBJECTIVE:** To test the hypothesis that a feeding-bundle concurrent with acid-suppression is superior to acid-suppression alone in improving gastroesophageal reflux disease (GERD) attributed-symptom scores and feeding outcomes in neonatal ICU infants.

**METHODS:** Infants (N=76) between 34-60 weeks' postmenstrual age with acid reflux index>3% were randomly allocated to study (acid suppressive therapy + feeding bundle) or conventional (acid suppressive therapy only) arms for 4 weeks. Feeding bundle included: total fluid volume <140 ml/kg/day, fed over 30 min in right lateral position, and supine postprandial position. Primary outcome was independent oral feeding and/or  $\geq 6$ -point decrease in symptom score (I-GERQ-R). Secondary outcomes included growth (weight, length, head circumference), length of hospital stay (LOHS, days), airway (oxygen at discharge), and developmental (Bayley scores) milestones.

**RESULTS:** Of 688 screened: 76 infants were randomized and used for the primary outcome as intent-to-treat, and secondary outcomes analyzed for 72 infants (N=35 conventional, N=37 study). For study vs conventional groups, respectively: a) 33%(95% CI, 19%-49%) vs 44%(95% CI, 28%-62%), p=0.28 achieved primary outcome success, and b) secondary outcomes did not significantly differ (p>0.05).

**CONCLUSIONS:** Feeding strategy modifications concurrent with acid suppression are not superior to PPI alone in improving GERD symptoms or discharge feeding, short-term and long-term outcomes.

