## STATISTICAL METHODS

Based on our preliminary data, we had planned to enroll 100 patients (50 per group) to detect 27% or higher increase in proportion of success of study group compared to the conventional group with 80% power and overall one-sided  $\alpha$  level of 0.025. One interim futility analysis was planned at about 50% information prior to the final analysis at 100% information, corresponding to 50 and 100 evaluable patients, respectively. The boundary was determined using Lan-DeMets spending functions to simulate O'Brein-Fleming boundaries(34). Using the target proportion of success, the boundary at the futility analysis was  $p>0.297$ .

Seventy-six infants were randomly assigned till the end of funding for this study and were included in the analysis of demographics and clinical characteristics (**Fig 1, Table 1**) and primary outcome by intent-to-treat. If a patient dropped out before the end of study and no symptom score was evaluable, we treated the patient as a failure for the primary outcome by intention-to-treat. Secondary outcome analysis was performed for 72 subjects (**Fig 1**). Futility boundary was not reached at interim analysis of 50 patients ( $p=0.1 < 0.297$ ) and accrual was continued with DSMB approval. Summary statistics were calculated for patient demographics and clinical characteristics for final analysis. Success rate in achieving PO or reduction in the I-GERQ-R by 6-points was calculated with 95% confidence interval and compared using chi-square test between the conventional and study groups (primary outcomes) for the intention-to-treat and treat-as-treated analyses. Fisher's exact or chi-square test were used to compare other categorical secondary outcomes including feeding method and supplemental oxygen between the groups. Shapiro-Wilk test for normality was used for the continuous outcomes. Paired t-tests or Wilcoxon singed-rank

tests were used to assess changes in growth velocity and feeding therapy characteristics between time-1 and time-2. Two sample t-tests or Wilcoxon rank-sum tests were used to compare these continuous outcomes between conventional and study groups. Median (interquartile range [IQR]), mean (SD), or % was reported, unless stated otherwise.  $P$  values  $<0.05$  were considered statistically significant, and SAS version 9.4 (SAS, Inc, an IBM Company, Chicago, IL) was used.

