*Salient features of our study include:* 1) Allocations were unbiased and appropriately distributed between groups. 2) Among those presenting with GERD symptoms at inception, about 36% of infants had normal esophageal acid exposure, while 40% had abnormal acid exposure, and the rest in the indeterminate range. 3) The study bundle was not superior to acid suppression alone in improving primary outcomes or secondary outcomes. 4) Restricted feeding volume, body positions (intra- and post-prandial), oral or gavage feeding methods, supplemental oxygen, birth gestation and postnatal maturation did not influence the primary or secondary outcomes. 5) Reliability of compliance among those discharged was based on parental trust and available information. 6) There were no reported adverse events. No differences in long term developmental outcomes or economic burden measures, such as, LOHS, feeding methods and respiratory support at discharge were noted. 7) Symptom scores (I-GERQ-R) were significantly lower in both groups, suggesting that maturation may play a role in symptom modification, and not the bundled approaches. 8) Feeding outcomes improved in both groups.

*GMT Trial strengths and clinical implications are several:* 1) Random allocation, study design and protocol adherence were robust and rigorous. Although our strict inclusion criteria may have led to lower eligibility, our approach resulted in identifying infants carefully with true ARI as a marker of esophageal acid exposure. Objective determination of GERD based on ARI >7%

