## **CONCLUSION**

We addressed the current practice controversies in this clinical trial: 1) Screening and identifying acid-GERD objectively is possible in symptomatic infants prior to any pharmacotherapy. 2) Feeding strategy modification (fluid restriction, positional changes, prolonged feeding duration) has no role in decreasing reflux-type symptoms or in improving the primary outcome of achieving independent oral feeds and/or a six-point decrease in I-GERQ-R score. 3) No difference in the prevalence of chronic lung disease was noted between the groups. 4) I-GERQ-R scores decreased across time regardless of treatment group allocations that strongly

support maturational effect. However, we did not detect an effect on *a priori* short-term or long-term outcomes following randomized allocations. As restrictive feeding strategies do not make a difference, placebo-controlled clinical trials in a larger cohort of convalescing NICU infants with objectively determined newer GERD criteria must be addressed in future trials.

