**Table 1. Baseline Demographic and Clinical Characteristics of Enrolled Participants**

Variable	Overall Subjects (N = 76)	Conventional Group (N = 36)	Study Group (N = 40)
At Birth			
Gender, Female – n (%)	37 (49)	18 (50)	19 (48)
Race – n (%)			
African American	11 (15)	3 (8)	8 (20)
Asian	1 (1)	0 (0)	1 (3)
Other	6 (8)	2 (6)	4 (10)
Unknown	1 (1)	1 (3)	0 (0)
White	57 (75)	30 (83)	27 (68)
Ethnicity – n (%)			
Hispanic or Latino	2 (3)	2 (6)	0 (0)
Non Hispanic or Latino	71 (93)	32 (89)	39 (98)
Unknown	3 (4)	2 (6)	1 (3)
Gestational Age (GA) – wks	29.3 [27 - 32.9]	29.3 [28 - 32.2]	29.2 [27 - 33.1]
Preterm birth – n (%)	68 (90)	34 (94)	34 (85)
Birth Weight – kg	1.23 [0.9 - 1.9]	1.2 [0.9 - 1.9]	1.3 [0.9 - 2.1]
Size for Gestational Age – n (%)			
Small (< 10th %)	9 (12)	5 (14)	4 (10)
Average (10th - 90th %)	58 (76)	26 (72)	32 (80)
Large (> 90th %)	9 (12)	5 (14)	4 (10)
Cesarean Delivery – n (%)	50 (66)	22 (61)	28 (70)
At Inception			
Postmenstrual age – wks	41.1 (2.5)	41.3 (2.2)	40.9 (2.7)
Chronologic age – wks	10.9 (4.3)	11.1 (4.5)	10.7 (4.3)
Weight – kg	3.5 (0.8)	3.5 (0.8)	3.5 (0.8)
O 2 Requirement at 36 wks PMA – n (%)	36 (47)	17 (47)	19 (48)
O 2 Requirement at 28 days age – n (%)	46 (61)	21 (58)	25 (63)
Feeding Method – n (%)			
Gavage	2 (3)	0 (0)	2 (5)
Transitional	37 (49)	18 (50)	19 (48)
Oral	37 (49)	18 (50)	19 (48)
Nasal Cannula Oxygen – n (%)	23 (30)	11 (31)	12 (30)
Total Intake Volume – mL/kg/day	150 [149 - 154]	150 [148 - 152]	150 [150 - 157]
Total Oral Intake Volume – mL/kg/day	112 [45 - 150]	112 [57 - 150]	112 [22 - 148]
Acid Reflux Index (ARI) – %	9.3 [6.0 - 17.1]	10 [6.0 - 16.7]	9.1 [5.0 - 17.6]
ARI Category – n (%)			
Indeterminate (ARI 3 - 7%)	26 (34)	12 (33)	14 (35)
Abnormal (ARI > 7%)	50 (66)	24 (67)	26 (65)

Data presented as n (%), Median [IQR], or Mean (SD).

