Receptive Communication <80 – n (%)	14/42 (33)	8/23 (35)	6/19 (32)	0.83
Receptive Communication Score – #	90 [77 - 103]	91 [74 - 103]	89 [77 - 103]	0.75
Expressive Communication <80 – n (%)	11/25 (44)	7/14 (50)	4/11 (36)	0.69
Expressive Communication Score – #	88 [71 - 100]	81 [71 - 94]	89 [71 - 103]	0.66
Fine Motor <80 – n (%)	11/41 (27)	5/23 (22)	6/18 (33)	0.49
Fine Motor Score – #	94 [79 - 103]	97 [82 - 110]	88 [70 - 97]	0.13

[figure not shown]
Data presented as n (%), Median [IQR], or Mean (SD). \*1 value missing from both conventional and study groups. †Data was not available for all subjects for long-term follow up outcomes, n values are reported.

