## 4.0 Study Endpoints

- Primary Outcome
  - **Clinical outcome of feeding success for those infants transitioning to oral feeds at inception.**
    - The primary endpoint is the feeding success defined as achieving full oral feeds (defined as no need for tube feeds to maintain hydration and nutrition) and/or a  $>/=$  6-point decrease from baseline I-GERQ-R. The time frame is up to 5 weeks after enrollment.
  - **Clinical outcome of feeding success for those infants on full oral feeds at inception.**
    - The primary endpoint is the feeding success defined as maintaining full oral feeds and a  $>/=$  6-point decrease from baseline I-GERQ-R. The time frame is up to 5 weeks after enrollment.
- Secondary Outcomes
  - Clinical Outcomes
    - Length of hospital stay
    - Growth outcomes during the study period and up to 1 year
    - Independent feeding skills over time up to 1 year
    - Respiratory support during the study period and at discharge
    - Developmental outcomes with Bayley's scores at 2 years
    - Individual differences in I-GERQ-R questionnaire
  - Motility Outcomes
    - Mechanisms of aerodigestive clearance and esophageal provocation are evaluated based on esophageal motility studies at inception and after 5 weeks.
  - pH Impedance outcomes
    - 24-hour pH impedance results at inception of study and then 5 weeks later after treatment completed

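### The single denominator of 72 for secondary outcomes does not apply to the long-term endpoints, which have 25 to 50 of 76 infants, so the long-term statements need their own n and should read as inconclusive

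*Combined protocol and SAP*

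**What the plan says.** The Abstract states "secondary outcomes analyzed for 72 infants (N=35 conventional, N=37 study"), names Bayley scores as one of those outcomes, and concludes that the bundle is not superior on short-term and long-term outcomes. Statistical Methods gives the same count: "Secondary outcome analysis was performed for 72 subjects".

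Table 2 heads its secondary-outcome block with N = 72 (35 and 37), but the rows under Long-term Follow-up carry smaller denominators. A footnote explains: "Data was not available for all subjects for long-term follow up outcomes, n values are reported". Section 4.0 Study Endpoints lists "Independent feeding skills over time up to 1 year" and Bayley scores at 2 years as secondary outcomes, so these rows are planned endpoints.

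The Discussion (salient features, item 6) says "No differences in long term developmental outcomes or economic burden measures" were noted. The Conclusion reports that no effect was detected on "short-term or long-term outcomes following randomized allocations". The limitations paragraph does not mention the incomplete long-term follow-up.

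We found no missing-data method for the long-term endpoints. The rule that counts a dropout as a failure is stated for the primary outcome.

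**The concern.** A reader of the Abstract will take the long-term conclusion to rest on 72 of 76 infants, which is close to complete follow-up. It rests on between one third and two thirds of those randomised. Two things follow. First, the comparisons are too imprecise to tell no difference from a sizeable one in either direction. Second, they are complete-case tests. They are unbiased only if the infants without long-term data resemble those with it in each arm, and the documents neither examine nor discuss this.

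At stake is what the trial can say about feeding after discharge and development at 2 years. The primary outcome (all 76 infants) and the discharge outcomes (72) do not depend on these rows.

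**Working it through.** **Inputs.** Randomised: "Conventional Group (N = 36") and "Study Group (N = 40") in Table 1. Secondary-outcome set: 35 and 37 (Abstract; Table 2 header). Long-term denominators: Table 2.

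**Step 1. Reproduce the stated figure.** 35 + 37 = 72, which agrees with the Table 2 header. It fits Time-2 feeding, feeding at discharge, oxygen at discharge and length of stay. It does not fit every in-hospital row: the I-GERQ-R decrease has 31 + 34 = 65, and the footnote to the length and head circumference velocities reports one value missing in each arm.

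**Step 2. Missing on the long-term endpoints.** Missing = randomised minus Table 2 denominator.

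| Endpoint | n (conv/study) | Missing of 76 | Missing, conv (of 36) | Missing, study (of 40) | Chi-square p |
|---|---|---|---|---|---|
| Feeding, 6 months | 50 (27/23) | 26 (34%) | 9 (25.0%) | 17 (42.5%) | 0.11 |
| Feeding, 1 year | 44 (22/22) | 32 (42%) | 14 (38.9%) | 18 (45.0%) | 0.59 |
| Bayley cognitive | 44 (23/21) | 32 (42%) | 13 (36.1%) | 19 (47.5%) | 0.32 |
| Bayley receptive | 42 (23/19) | 34 (45%) | 13 (36.1%) | 21 (52.5%) | 0.15 |
| Bayley expressive | 25 (14/11) | 51 (67%) | 22 (61.1%) | 29 (72.5%) | 0.29 |
| Bayley fine motor | 41 (23/18) | 35 (46%) | 13 (36.1%) | 22 (55.0%) | 0.10 |

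The p-values are uncorrected chi-square tests of missing against arm. Fisher's exact test gives 0.11 to 0.65. The direction is the same against the 35/37 base: 8 vs 14, 13 vs 15, 12 vs 16, 12 vs 18, 21 vs 26 and 12 vs 19. The gap at 1 year then shrinks to 3.4 points (13/35 = 37.1% vs 15/37 = 40.5%).

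**Step 3. Precision for full oral feeding, study minus conventional.** Newcombe interval: with d = p1 - p2 and Wilson limits (l, u) for each arm, lower = d - sqrt[(p1 - l1)^2 + (u2 - p2)^2] and upper = d + sqrt[(u1 - p1)^2 + (p2 - l2)^2].

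- 6 months: p1 = 15/23 = 65.2% (Wilson 44.9 to 81.2); p2 = 21/27 = 77.8% (59.2 to 89.4). d = -12.6 points. Lower = -12.6 - sqrt(20.3^2 + 11.6^2) = -36. Upper = -12.6 + sqrt(16.0^2 + 18.5^2) = +12.
- 1 year: p1 = 17/22 = 77.3% (56.6 to 89.9); p2 = 20/22 = 90.9% (72.2 to 97.5). d = -13.6 points. Lower = -13.6 - sqrt(20.7^2 + 6.6^2) = -35. Upper = -13.6 + sqrt(12.6^2 + 18.7^2) = +9.

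**Step 4. Extreme bounds.** These set every missing infant against one arm and then against the other.

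- 6 months: 15/40 - 30/36 = -46 points; 32/40 - 21/36 = +22 points.
- 1 year: 17/40 - 34/36 = -52 points; 35/40 - 20/36 = +32 points.

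These are limits on what the data exclude. They are not estimates of likely bias.

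**The case against.** The strongest reply is that nothing is concealed and little is over-claimed. Table 2 prints the denominators by arm and footnotes the shortfall. The Abstract says not superior, and the Conclusion says no effect was detected; neither asserts equivalence. Both long-term feeding estimates are lower in the study arm, which fits non-superiority. Figure 1 is not reproduced in the text we have and may give follow-up counts. All of this stands, and it limits the point to reporting. Only the Discussion item puts the result flatly as no differences. But a footnote does not correct a denominator stated in the Abstract and Statistical Methods, and the limitations paragraph is silent on the loss.

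A reader might also infer from the missing counts that attrition biased the long-term comparison. The documents do not support that. No imbalance is significant. The six endpoints concern overlapping infants, and four are scores from one assessment, so a consistent direction is not six independent signals. The larger study arm inflates raw counts, and at 1 year both arms have 22 infants. Reasons for missing data are not given. Follow-up ran to October 2018 with data lock in May 2019, so some late enrollees may not have reached the later visits.

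Nor do the data show that the bundle worsened long-term feeding: both intervals include zero.

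**Conclusion.** The point holds as a reporting correction that should be made. The figure of 72 is right for most in-hospital secondary outcomes and wrong for every long-term one, where n is 25 to 50 and 34% to 67% of randomised infants are missing. The excess missing in the study arm (6 to 19 points against 36/40) is a risk of bias and no more. Intervals reaching -36 and +12 points at 6 months, and -35 and +9 at 1 year, make the long-term feeding result inconclusive.

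This assumes that the Table 2 denominators were read correctly from the PDF. A further Bayley row could have been lost in extraction, but that would not change the rows shown. The primary outcome is unaffected.

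**What to change.** 1. In the Abstract and Statistical Methods, replace the single N of 72 with n by endpoint and arm: 72 (35/37) for the in-hospital outcomes where it applies, 65 (31/34) for the I-GERQ-R decrease, and the Step 2 values for each long-term endpoint.
2. Report the long-term differences with 95% confidence intervals, as in Step 3.
3. Add the incomplete long-term follow-up, by arm and with reasons where known, to the limitations paragraph.
4. Reword the long-term statements in the Abstract, Discussion item 6 and Conclusion to say that no difference was detected among infants followed and that the long-term data are inconclusive.
5. Optional sensitivity analysis: a random-effect logistic model of full oral feeding at Time 2, discharge, 6 months and 1 year, in the 72 infants with at least one feeding observation, adjusted for feeding route at inception, with the Step 4 bounds shown beside it. The other four randomised infants have no reported feeding outcome. An unweighted GEE would not be a good substitute, because it generally needs data missing completely at random. Imputing Bayley scores with 42% to 67% missing would lean heavily on its assumptions, so we do not ask for it.

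Items 1 to 4 need no new data and cost only a weaker long-term statement, plus a check of the records for reasons. Item 5 is a modest extra analysis of data already held.

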## **INTRODUCTION**

Differentiating gastroesophageal reflux (physiological, GER) from GER disease (pathological, GERD) remains a challenge in ICU infants (1-5). Troublesome symptoms (6) often trigger a battery of empiric therapies, such as acid-suppression, feeding modifications, and positional changes (7-10). Prevalence of GERD ranges from 2–30% across neonatal intensive care unit(NICU)s in the United States, along with a 13-fold variation in therapies, imposing an additional economic burden of over \$70K per admission and 30 hospital days (9-13).

The infant GER questionnaire-revised (I-GERQ-R) is a survey of parental/provider perception of symptom burden thought to be due to GERD, with a 6 point decrease indicating clinical improvement (14). Although, prior clinical trials for GERD pharmacotherapy have used symptom-based criteria (15-18), few have evaluated the effectiveness of a bundled holistic approach, i.e., a combination of pharmacologic-, feeding-, and positional approaches in NICU patients. Improvement of parental perception of symptoms and total GER events with left lateral position and proton pump inhibitor (PPI) (8), reduction of GER events with infants in prone or left lateral post-prandially (19), and conservative strategies for 2 weeks showed improvement with I-GERQ-R scores among one to ten months age (20). We observed that decreased feeding volume and prolonged feeding duration were associated with reduced GER events (21). However, a bundled approach combining targeted acid suppression (limited duration), feeding modifications (volume, position, duration) and postprandial positions has not been rigorously examined in infants with proven esophageal acid reflux index (ARI) severity.

Based on this *rationale*, we have undertaken this clinical trial to determine the effective therapeutic strategies on the clinically meaningful primary outcomes in infants presenting with GERD symptoms who have qualifying ARI criteria. The *objective* of this RCT was to examine the

short- and long-term clinical outcomes among infants treated concurrently over 4 weeks with PPI with randomly assigned feeding strategy modifications while controlling for gestational maturity (pre-term or full-term at birth) and severity of esophageal ARI (3-7%, >7%). Our *hypothesis* was that the study approach (acid suppression, modified feeding volume, duration, and position) was superior in achieving independent oral feeding or a 6-point reduction in I-GERQ-R vs the conventional (acid suppression alone) feeding approach.

## **PATIENTS AND METHODS**

### **STUDY DESIGN AND EXPERIMENTAL PROTOCOL**

This is a single center, single blinded RCT (Clinicaltrials.gov: [NCT02486263](#)) comparing the effectiveness of two feeding strategies combined with the use of a PPI (omeprazole) to manage acid-GERD [GERD Management and Therapy trial (GMT trial)]. This study was approved by the Institutional Research Board (IRB) at Nationwide Children's Hospital, Columbus, OH (IRB # 11-00734). Omeprazole is commonly used off-label in this population within the standard of care (9). Data safety monitoring plan was implemented and monitored quarterly by the Data Safety Monitoring Board (DSMB). Written, signed, and informed parental consent was obtained. Health Insurance Portability & Accountability was followed. Study PI and RN coordinator were available 24/7.

Twenty-four-hour pH-impedance studies were performed (6, 22, 23) (Laborie Medical Technologies, Mississauga, ON, Canada). ARI (duration of esophageal acid exposure, %) was calculated (24). I-GERQ-R symptom score (14, 17, 25) was collected. Demographic and clinical outcomes were managed using research electronic data capture tools (REDCap) tools (26) for up to 2 years from subject enrollment.

### **PARTICIPANT SELECTION, RANDOMIZATION AND ALLOCATION**

Inclusion criteria were: a) infants admitted with clinical symptoms of GERD between 34-60 weeks postmenstrual age, with physician's intent to treat with acid-suppressive therapy, b) an intake volume of full enteral feeds  $\geq 150$  mL/kg/day, c) room air or supplemental oxygen  $\leq 1$  liter per minute, and d) ARI  $\geq 3\%$  (6, 22-24). Exclusion criteria were: a) infants with known genetic, metabolic or syndromic diseases; b) neurological diseases including  $\geq$  grade III intraventricular hemorrhage or perinatal asphyxia, c) GI malformations or surgical GI conditions, and d) infants on acid suppressive medication at initial evaluation. Randomization was performed among consented subjects who were stratified 1:1 ratio by ARI severity (3%-7%: indeterminate acid reflux and  $>7\%$ : severe acid reflux) and by birth gestation (preterm, full term) into study feeding approach or conventional approach. Permuted Block Randomization with block sizes of 2, 4, 6, and 8 was undertaken by the study statistician (OSU Center for Biostatistics) using a computer-generated allocation and implemented in REDCap. Nurse coordinator enrolled subjects by verifying eligibility, obtaining parental consent, and entering demographic data into REDCap. PI and study staff who evaluated subject clinical outcomes were blinded to study allocation.

